The primary endpoint is to evaluate the **safety and tolerability** of concurrent single/low dose radiotherapy (8 Gy/1fx) in combination with pembrolizumab in relapsed and/or refractory myeloma patients at 3 months (**acute toxicity, primary endpoint**) and at 6 and 12 months (**late toxicity**). The secondary objective is to characterize the effect of radiation in combination with pembrolizumab on systemic response rates using international myeloma working group (IMWG) uniform response criteria for myeloma, to assess baseline changes in PET/CT as a result of combining pembrolizumab and radiotherapy, and to evaluate treatment response at irradiated and un-irradiated sites (i.e. the abscopal effect) using baseline PET/CT. Exploratory analysis would include analyzing Circulating Myeloma Tumor cells and phenotype of T cells as a prognostic and predictive biomarker. Compare blood Myeloma tumor cells with BM tumor cells. We are interested in comparing T cell phenotype after each treatment and using that as a prognostic biomarker. We will also evaluate serum LDH, CRP, ESR, ALC, cytokines and chemokines (such as IL-6, s IL-6R) and other immune related biomarkers, and correlate their expression pre and post treatment and evaluate changes in bone marrow biopsy and peripheral blood for mutational load, mutational signature (whole exome sequencing), transcriptome of the T cells, mutation specific T cells, PD1 and PDL1 expression on MM cells and T cells by flow/IHC, RNA-seq. Other biomarker correlative exploratory analysis (role of exosomes, etc) may also be pursued as ancillary research to this trial;

2. Acute Toxicity and Late Toxicity Assessment:

[figure not shown]
Acute toxicity (i.e. > Grade 2 CTCAE toxicity at **3 months**) associated with radiation therapy at the **radiated site** will be analyzed as the **primary safety endpoint** in this pilot study; Goal would be to see less than 20% > grade 2 toxicity at 3 months within the radiated area.

CTCAE criteria (see Appendix I) will be applied to assess acute toxicity.

Other endpoints that may be analyzed include late toxicity (> Grade 2 CTCAE toxicity at the radiated site at **6 months and 12 months**), systemic response against myeloma burden to localized radiation and pembrolizumab using IMWG uniform criteria, as well as other endpoints (defined in more detail in section 3.0).

3. Trial Schema

Figure 1: Trial Overview

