3. OBJECTIVES, ENDPOINTS & HYPOTHESES

1. Primary Objective, Endpoint, & Hypothesis

Primary Objective

To evaluate the safety of concurrent single/low dose radiotherapy (**8 Gy/1fx**) in combination with Pembrolizumab in relapsed or refractory myeloma patients; **Once 10 patients are enrolled, we will stop trial for 3 months to assess for acute toxicity, and then resume the trial.**

Primary Endpoint

CTCAE > grade 2 toxicity at the specific irradiated **organ site at 3 months** (the Dose Limiting Toxicity);

Primary Hypothesis

The primary hypothesis of this pilot study is that the use of concomitant Pembrolizumab and radiation therapy in multiple myeloma patients will be well tolerated and safe.

Alternative Hypothesis

It is possible that concurrent use of radiotherapy and Pembrolizumab in relapsed/refractory myeloma may increase CTCAE > grade 2 toxicity within the radiated site at 3 months.

2. Secondary Objective(s), Endpoint(s) & Hypothesis (es)

Secondary Objectives

To characterize late toxicity (CTCAE > grade 2 toxicity at **6 and 12 months**) and the effect of radiation in combination with Pembrolizumab on systemic response rates using international myeloma working group (IMWG) uniform response criteria for multiple myeloma at **6 months and 12 months**;

To assess changes in PET/CT as a result of combining Pembrolizumab and radiotherapy at **6 months and 12 months**;

Secondary Endpoints

- a. 1. Number of patients achieving any response (from baseline) per IMWG response criteria at **6 months and 12 months**;
- b. 2. Overall survival time at **6 months and 12 months**;
- c. 3. Overall response based on baseline changes on PET/CT at **6 months and 12 months**;
- d. 4. Difference in pre and post treatment serum immune biomarkers;

Secondary Endpoint Definitions

- a. Response is defined per IMWG criteria, and will be calculated at **6 months and 12 months**;
- b. Overall survival will be defined as time from first treatment on cycle 1, day 1 to the earlier of date of death and/or last follow up at **6 months and 12 months**.
- c. Overall response will be defined using IMWG uniform response criteria.
- d. Several serum biomarkers will be analyzed.

Secondary Hypotheses

The secondary hypothesis is that low dose/single fraction (8Gy/1fx) will synergize with Pembrolizumab for a more effective anti-myeloma response per IMWG, via the radiation induced abscopal response.

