post-treatment follow-up for disease status until disease progression, initiating a non-study cancer treatment, withdrawing consent or becoming lost to follow-up. After documented disease progression each subject will be followed by telephone for overall survival until death, withdrawal of consent, or the end of the study, whichever occurs first.

Discontinuation of Study Therapy after CR

Discontinuation of treatment may be considered for subjects who have attained a confirmed CR that have been treated for at least 24 months with pembrolizumab and had at least two treatments with pembrolizumab beyond the date when the initial CR was declared. Subjects who then experience radiographic disease progression may be eligible for up to one year of additional treatment with pembrolizumab via the Second Course Phase at the discretion of the investigator if no cancer treatment was administered since the last dose of pembrolizumab, the subject meets the safety parameters listed in the Inclusion/Exclusion criteria, and the trial is open. Subjects will resume therapy at the same dose and schedule at the time of initial discontinuation.

Clinical Criteria for Early Trial Termination

Early trial termination will be the result of the criteria specified below:

- 1) Quality or quantity of data recording is inaccurate or incomplete
- 2) Poor adherence to protocol and regulatory requirements
- 3) Incidence or severity of adverse drug reaction in this or other studies indicates a potential health hazard to subjects
- 4) Plans to modify or discontinue the development of the study drug

In the event of Merck decision to no longer supply study drug, ample notification will be provided so that appropriate adjustments to subject treatment can be made.

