selection ranging from 4 MeV – 20 MeV. For deeper seated tumors, photon therapy should be used with energy range of 4MV – 18 MV, based on appropriate coverage of the PTV. The goals should be to provide adequate coverage, while minimizing hot spots as well as scattered radiation dose to the surrounding structures.

A range of radiation fields are allowed. A single beam, an AP/PA, or multiple beams are allowed. A range of radiation techniques (2D, 3DCRT, IMRT, IMRS) are allowed;

Institutional standard of care protocol will be followed when assessing adequate PTV coverage and dose volume histogram normal tissue limits.

Radiation Toxicity Evaluation

Patients should undergo evaluation for development of acute and chronic radiotherapy toxicity at the time of protocol visits. This should be done at **1 month +/- 2 weeks** after completing radiotherapy and **every 3 months for at least 1 year**. Toxicity will be graded per CTCAE 4.0 adverse events grading system. If there is a suspicion of a novel or unexpected toxicity of grade 3 or higher severity that is suspected to be related to the combination of pembrolizumab and radiotherapy, the study coordinator should be immediately notified. If possible, a determination should be made whether the toxicity is likely to be the result of immune therapy, radiotherapy, or was exacerbated by the combination. The AE or SAE should be attributed as definite, probable, possible, or unlikely for each.

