11. STATISTICAL ANALYSIS PLAN

1. Statistical Analysis Plan Summary

Study Design

The study is a pilot study to look at the safety of concurrent PD-1 inhibitor and SRS for relapsed/refractory myeloma. A total of 24 patients will be enrolled on the trial (20 is the minimum, with an additional 4 patients, to make for any attrition and/or loss to follow-up). 12 patients will be allowed to not have measurable myeloma disease in this trial. Once 10 patients are enrolled, we will stop trial for 3 months to assess for acute toxicity, and then resume the trial. The estimated exact Clopper-Pearson 95% confidence interval for a 20% rate based on 5 responses in 20 patients is (0.087, 0.491), with a precision of 0.185. If we see lower than 20% difference in rate of toxicity at 3 months, the combination will be deemed safe.

A minimum of 20 patients are required to complete full treatments. An additional 20% is allowed for drop out/failure to adhere to required follow-up and treatment recommendations. Thus, 24 patients will be allowed to be enrolled on the trial to make for any attrition and/or loss to follow-up. 12 patients will be allowed to not have measurable myeloma disease.

# of Responses / # of Patients	95% confidence interval
5 / 20	(0.087, 0.491)
6 / 24	(0.098, 0.467)

Populations for analysis

- Enrolled set: All subjects who signed an informed consent.
- Safety set: All subjects who received at least one dose of any study drug.
- Full analysis set: All subjects from the safety set who have the required follow-up and treatment adherence to evaluate response and safety over time.

2. Statistical Analyses

1. Response

IMWG criteria will be used to assess response. Proportion of patients achieving stable

disease or better will be reported at **6 months** and **12 months**; Response rates will be reported along with 95% confidence intervals will be estimated using the Clopper-Pearson method.

2. Safety

Proportion of acute (at **3 months**) and late toxicity (**6 and 12 months**) will be reported, and 95% confidence intervals will be estimated using the Clopper-Pearson method.

3. Overall Survival

For overall survival, death from any cause will be defined as the event. Patients will be censored at time of last follow-up. OS will be estimated using the Kaplan-Meier product-limit method. Overall survival will be analyzed at **6 months, and 12 months**.

4. Biological variables

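### The sentence that declares the combination safe rests on a toxicity difference with no comparator, conflicts with the absolute below-20% goal in Section 2, and leaves the 10-patient pause without a criterion

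*Combined protocol and SAP*

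**What the plan says.** Section 11, Study Design, states the decision rule: "If we see lower than 20% difference in rate of toxicity at 3 months, the combination will be deemed safe". It names no reference rate, toxicity grade or body site.

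Section 2, under Acute Toxicity and Late Toxicity Assessment, sets the target for the primary safety endpoint: "Goal would be to see less than 20% > grade 2 toxicity at 3 months within the radiated area". Section 3 defines that endpoint as "CTCAE > grade 2 toxicity at the specific irradiated" site, read at 3 months. Its alternative hypothesis says only that toxicity may rise and gives no baseline. The Protocol Summary lists the type of control as none.

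The Safety paragraph of Section 11 says the proportions with acute and late toxicity "will be reported, and 95% confidence intervals will be estimated using the Clopper-Pearson method". Of the analysis sets, it describes one as "Full analysis set: All subjects from the safety set who have the required follow-up and treatment adherence to evaluate response and safety over time", but the verdict sentence names no set.

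On the interim look, Section 3 says: "Once 10 patients are enrolled, we will stop trial for 3 months to assess for acute toxicity, and then resume the trial". Section 11 repeats this.

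**The concern.** A difference needs two rates, and this single-arm trial yields one. Someone following Section 11 literally would have to supply the second rate, possibly after seeing the data. Someone following Section 2 would compare one observed rate with 20%. In a trial of 20 to 24 patients the two can give opposite verdicts on the same data.

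The pause is written as stop, assess, resume. Neither Section 3 nor Section 11 says what finding would prevent resumption, or who decides, even when the first 10 patients have already put Section 2's goal out of reach.

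**Working it through.** **The plan's own figures.** Exact Clopper-Pearson 95% limits for 5/20 are 0.087 to 0.491, and for 6/24 they are 0.098 to 0.467. Both reproduce. Both are intervals for a single proportion, not for a difference.

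**Inputs.** Patients: 20 minimum, 24 enrolled (Section 11). Margin: 20% (Sections 2 and 11). Reference rate r: none designated, so every value below is an assumption. Section 4.4 reports grade 3-4 pembrolizumab toxicity in other studies, but those rates are systemic, not for the irradiated site, and are not named as a benchmark.

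**Step 1: largest count that passes.** Absolute rule: largest x with x/n < 0.20.
- n = 20: 3/20 = 15.0% passes; 4/20 = 20.0% fails.
- n = 21 to 24: 4 passes (4/24 = 16.7%); 5 fails (5/24 = 20.8%).

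Difference rule: largest x with x/n − r < 0.20, that is x < (0.20 + r)n. For r = 10% and n = 24, x < 7.2, so 7.

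| Assumed r | n=20 | n=21 | n=22 | n=23 | n=24 |
|---|---|---|---|---|---|
| 0% (same as absolute rule) | 3 | 4 | 4 | 4 | 4 |
| 1% | 4 | 4 | 4 | 4 | 5 |
| 3% | 4 | 4 | 5 | 5 | 5 |
| 5% | 4 | 5 | 5 | 5 | 5 |
| 10% | 5 | 6 | 6 | 6 | 7 |
| 15% | 6 | 7 | 7 | 8 | 8 |
| 20% | 7 | 8 | 8 | 9 | 9 |

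Up to a 5% reference the shift is at most one event. The 20% row equals Section 2's own ceiling and is shown only as the extreme.

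**Step 2: chance of a safe verdict at a true rate of 30%,** binomial P(X ≤ x).
- Absolute rule: P(X ≤ 3 of 20) = 0.107; P(X ≤ 4 of 24) = 0.111.
- r = 1 to 5%: P(X ≤ 4 of 20) = 0.238; P(X ≤ 5 of 24) = 0.229.
- r = 10%: P(X ≤ 5 of 20) = 0.416; P(X ≤ 7 of 24) = 0.565.

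**Step 3: denominator.** Suppose 24 patients are treated, 20 are evaluable and all 4 events fall among the evaluable. The safety-set rate is 4/24 = 16.7%, which meets the goal. The full-analysis-set rate is 4/20 = 20.0%, which does not.

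**Step 4: the pause.** With 5 events in the first 10 patients, the best possible final result at 24 is 5/24 = 20.8%, so Section 2's goal is already lost. P(X ≥ 5 of 10) is 0.033, 0.150 and 0.367 at true rates of 20%, 30% and 40%. Four events in 10 rule the goal out only if no more than 20 patients are evaluable (4/20 = 20.0%; 4/21 = 19.0%).

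**The case against.** The best defence is that *difference* is one loose word. There is no control, Section 2's goal is absolute, the endpoint in Section 3 contains no comparison, and the Safety analysis is a single proportion with its interval. Read together, these support one workable rule, an observed rate below 20%, and on that reading no count changes. The rate and interval will be reported whatever label is attached. That is probably what was meant, but the verdict sentence says something else and also omits the grade and the site.

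The larger probabilities depend on assumed references of 10% or more. That is fair. With a one-event shift, the two rules disagree only when exactly 4/20 or 5/24 occurs. The probability of that is about 9% and 6% at a true rate of 10%, 22% and 20% at a true rate of 20%, and 13% and 12% at 30%. So the effect is small if toxicity is low and material near the margin.

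On the denominator, the wording of the full analysis set points to that set, so this is a missing assignment rather than a contradiction, and 4/24 against 4/20 is a boundary case.

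On the pause, general safeguards exist. Section 7 allows early termination if "Incidence or severity of adverse drug reaction in this or other studies indicates a potential health hazard to subjects". Section 8 says that for a suspected novel or unexpected toxicity of grade 3 or higher "that is suspected to be related to the combination of pembrolizumab and radiotherapy, the study coordinator should be immediately notified". Section 10 requires rapid event reporting. Section 13.0 provides committee review of safety and aggregate toxicity, every 6 months or annually by risk level. Section 2's figure is also a goal, not a stopping boundary, so losing it does not by itself make resumption wrong. This stands, and it makes the pause the smaller gap. Still, none of these provisions is linked to the decision to resume.

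**Conclusion.** The concern holds. The only sentence that turns the primary endpoint into a safety conclusion cannot be applied as written, and it does not match the goal stated for the same endpoint in Section 2. This must be corrected, whether or not the word is a slip.

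The size of the discrepancy depends on a reference rate the documents do not supply. Assumed references of 1 to 5% move the cut-off by at most one event; at n=20 or n=24 that one event roughly doubles the chance of passing a true 30% rate, from about 11% to 23 or 24%. A 10% reference raises it to 42% (n=20) or 56% (n=24). These probabilities assume independent patients with a common toxicity rate.

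The missing criterion at the pause and the unassigned analysis set are real but lesser gaps.

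**What to change.** **Verdict sentence (Section 11).** Replace it with Section 2's criterion: the acute toxicity goal is met if fewer than 20% of patients have CTCAE toxicity above grade 2 at the radiated site at 3 months (at most 3 of 20, or 4 of 21 to 24), reported with its Clopper-Pearson 95% interval. Speaking of a goal being met, rather than of safety being shown, follows Section 2's own term. It also suits the precision available: the upper limits at the largest passing counts are 37.9% (3/20) and 37.4% (4/24). If an excess over a reference rate is really intended, name the rate and its source and change Section 2 to agree.

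**Denominator (Section 11).** State which defined set carries the verdict and report the rate in the other beside it. The present wording points to the full analysis set. The same edit should say whether the endpoint counts toxicity present at the 3-month visit or any occurring up to it, since the flow chart note in Section 9 has it assessed once at that time.

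**Pause (Sections 3 and 11).** Make resumption conditional on a documented review of the 10 patients' 3-month assessments, against a criterion that the sponsor and the monitoring committee set in advance and reconcile with Section 2's goal and Section 7's termination criteria. No numeric threshold is proposed here.

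**Cost.** A few sentences, agreement between the sponsor and the committee on the criterion, and possibly a slightly longer pause. No extra patients or assessments.

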1. PROTOCOL SUMMARY

Abbreviated Title	Pilot Study of Pembrolizumab and Single-fraction, Low-dose, Radiation Therapy in Patients with Relapsed or Refractory Multiple Myeloma
Trial Phase	Pilot Study
Clinical Indication	Relapsed or Refractory Multiple Myeloma
Trial Type	Pilot study
Type of control	None
Route of administration	Patients will receive on day 1, cycle 1 , radiotherapy (8 Gy/1fx) to an extra-osseous or osseous myeloma site followed by pembrolizumab (200 mg/kg i.v. on day 2 or 3 , then every 3 weeks +/- 7 days).
Trial Blinding	N/A
Number of trial subjects	24 patients (20 patients minimum, with 4 extra patients to account for loss to follow-up/attrition and/or failure to comply with recommended treatments); 12 patients will be allowed to not have measurable myeloma disease.
Estimated enrollment period	2 years
Description of enrollment	Following evaluation by medical oncology and radiation oncology, patients will be enrolled. Baseline assessment prior to enrollment may include bone marrow biopsy, peripheral blood collection, and staging of the patient per standard of care. Baseline serum and urine paraprotein analysis, bone marrow biopsy, PET/CT imaging, routine blood work, and baseline physical exam prior to enrollment. Patient with measurable myeloma disease will be screened for tolerability to Pembrolizumab and radiotherapy. Patients will be assessed at 1st month and every 3 month for response using the standard International Myeloma Working Group (IMWG) Response Criteria, and will undergo routine myeloma labs every 6 weeks until progression or as clinically indicated ; Patients with stable disease or better per IMWG response criteria will continue with maintenance pembrolizumab (200 mg/kg every 3 weeks for 2 yrs) . Patients that have progressive disease, or relapse after a complete response will be removed from the trial and treated per standard of care at the discretion of the treating physician.
Duration of Intervention	At least 24 months of Pembrolizumab, or until progression.
Duration of Evaluation	3 year (2 yrs for accrual, and at least 1 year follow-up for the last patient accrued on the study)
Estimated duration of trial	3 years (2 years to accrue + 1 years to follow all patients)
Duration of Participation	3 years
Study Center	Emory University. Atlanta, Georgia.

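### The safety verdict rests on an observed rate below 20% with no assigned denominator, and claims more than the planned exact interval can support

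*Combined protocol and SAP*

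**What the plan says.** The primary endpoint in Section 3 is "CTCAE > grade 2 toxicity at the specific irradiated" organ site at 3 months. Section 2 (Acute Toxicity and Late Toxicity Assessment) sets the aim: "Goal would be to see less than 20% > grade 2 toxicity at 3 months within the radiated area". Section 11 (Study Design) turns that aim into a verdict: "If we see lower than 20% difference in rate of toxicity at 3 months, the combination will be deemed safe".

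The Protocol Summary records "Type of control None", so the word difference in the Section 11 rule has nothing to be measured against. I read it as the absolute rate in Section 2.

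On numbers, Section 11 says "A total of 24 patients will be enrolled on the trial (20 is the minimum, with an additional 4 patients" being for attrition. It adds "A minimum of 20 patients are required to complete full treatments" and "An additional 20% is allowed for drop out/failure to adhere to required follow-up and treatment recommendations". Three populations are defined there: an enrolled set, a safety set (at least one dose) and a full analysis set (safety-set patients with the required follow-up and treatment adherence). The last is described as serving the evaluation of both response and safety. The Safety paragraph promises toxicity proportions with 95% Clopper-Pearson intervals. It does not say which population is used, and no confidence limit enters the verdict.

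**The concern.** The rule converts a point estimate from about two dozen patients into a statement that the combination is safe. Near the threshold, the interval the SAP itself plans to report will include rates far above 20%, so the verdict and the interval will say different things about the same data.

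The unassigned denominator adds to this. One of the two candidate populations drops patients for non-adherence. A patient who stops treatment because of toxicity could then leave the numerator as well as the denominator, and around 20% a single such exclusion can change the verdict. Section 4 says that the pilot is meant to guide later trial designs and clinical decisions, so an overstated conclusion would be carried forward.

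**Working it through.** **Inputs.** Threshold: strictly below 20% (Sections 2 and 11). Analysed number n: 20 to 24 (Sections 1 and 11). Interval: two-sided 95% Clopper-Pearson (Section 11). The true rates of 10%, 20% and 30% are my assumptions, to show the range.

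**The plan's own figures.** The lower limit is the 0.025 quantile of Beta(x, n−x+1); the upper limit is the 0.975 quantile of Beta(x+1, n−x).

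- 5/20 gives 0.0866 to 0.4910, and 6/24 gives 0.0977 to 0.4671. Both match Section 11.
- The text around them does not match. 5/20 is 25%, not 20%; an observed 20% is 4/20, with interval 0.057 to 0.437. The stated precision of 0.185 is the half-width for 6/24, (0.4671 − 0.0977)/2 = 0.1847. For 5/20 it is (0.4910 − 0.0866)/2 = 0.2022. These are side points and do not affect what follows.

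**Passing counts and intervals.** For each n, let c be the largest whole number with c/n < 0.20. The chance of passing at true rate p is the sum over x = 0 to c of C(n,x) p^x (1−p)^(n−x). For n = 20 and p = 0.20: 0.0115 + 0.0576 + 0.1369 + 0.2054 = 0.411.

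| n | passes if events ≤ | rate at that count | exact 95% interval | P(pass), true 10% | true 20% | true 30% |
|---|---|---|---|---|---|---|
| 20 | 3 | 15.0% | 3.2% to 37.9% | 86.7% | 41.1% | 10.7% |
| 21 | 4 | 19.0% | 5.4% to 41.9% | 94.8% | 58.6% | 19.8% |
| 22 | 4 | 18.2% | 5.2% to 40.3% | 93.8% | 54.3% | 16.5% |
| 23 | 4 | 17.4% | 5.0% to 38.8% | 92.7% | 50.1% | 13.6% |
| 24 | 4 | 16.7% | 4.7% to 37.4% | 91.5% | 46.0% | 11.1% |

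**Sensitivity to the inequality.** If the rule were at most 20%, 4/20 would also pass. The chance of passing at a true 20% would then run from 46.0% (n = 24) to 63.0% (n = 20). The text says lower than, so the table uses the strict form.

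**Choice of population.** Two illustrations, each with 24 treated:

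- Five events, one of them in a patient later excluded for non-adherence: safety set 5/24 = 20.8%, fails; full analysis set 4/23 = 17.4%, passes.
- Four events, and four event-free patients excluded: safety set 4/24 = 16.7%, passes; full analysis set 4/20 = 20.0%, fails.

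The choice of set can therefore move the verdict in either direction.

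**The case against.** The strongest reply is that this is a pilot. It states no alpha or power and calls 20% a goal. Any rule that compares an observed proportion with 20% passes roughly half the time when the truth is exactly 20%. The exact interval will be reported anyway. Nor is the verdict the only safeguard: there is a 3-month pause after 10 patients (with no numerical boundary), early termination for the incidence or severity of adverse reactions (Section 7), and committee review of aggregate toxicity (Section 13). Much of this stands. A pilot need not control error rates, and nothing here calls for more patients or a formal test. What it does not answer is that the SAP chose to attach a declaration of safety to this rule, and that the planned interval will not bear that declaration out.

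A reader might go further and infer that the investigators could see 4/20, add an event-free 21st patient and pass with 4/21. The documents do not support this:

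- Sections 1, 10 and 11 plan for 24 enrolled, and the 20 is most naturally the number left after attrition. Only one phrase in Section 11, that 24 will be allowed, points the other way.
- The endpoint is read at 3 months. If 24 patients accrue evenly over 24 months (an assumption), about three would not yet have reached 3 months when the 21st enrols. A final 4/20 would not normally be known then.
- The pass rate under such optional addition, 0.4114 + 0.2182 × 0.80 = 0.586, is simply the fixed n = 21 value. It shows no separate effect of looking at the data.

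A reader might also want safety declared only when the upper limit is below 20%. With the planned interval that requires zero events (0/20 has an upper limit of 16.8%; 1/24 already reaches 21.1%). At a true rate of 5% this would be met only 0.95^20 = 36% of the time with 20 patients, or 0.95^24 = 29% with 24. It is too strict to impose on this design.

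**Conclusion.** The concern holds, as a should-fix. A result can be declared safe while its exact interval extends to about 37% to 42%, and the plan leaves open which patients are counted. How often a truly 20% or 30% toxic regimen passes depends on the final n, as the table shows; equally, a regimen with a true 10% rate passes 87% to 95% of the time, so the rule is informative but cannot establish a rate below 20%.

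This rests on reading the rule as an absolute rate strictly below 20%, on independent patients with a common true rate, and on 20 to 24 being analysed. The pause after 10 patients is left out of the calculation because it has no boundary. The exclusion examples show what the wording permits; they do not predict what will happen.

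**What to change.** 1. In Section 11, make the safety set (all treated patients, once accrual has closed) the decision set for the 3-month toxicity rate. Write the limit as a count for its size: at most 3 events if N = 20, at most 4 if N = 21 to 24. Remove the word difference. State how a treated patient without a 3-month assessment is counted, since that patient now stays in the denominator.

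2. Replace the declaration that the combination is safe with a statement that the observed rate meets the below-20% goal. Report it with its exact 95% interval, and add that this does not show the true rate to be below 20%.

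The cost is SAP wording only: no extra patients, visits or analyses. The counts are the existing threshold made explicit, so the pass rates for a given N do not change. What changes is that the denominator is fixed in advance and the conclusion matches the data. The downside is a more modest conclusion.
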